**Please save frequently**

e) State if deception (including incomplete disclosure of study purpose/procedures) will be used. If so, describe the nature of the deception and provide a rationale for its use. Also, describe debriefing procedures or justify a waiver of the requirement to debrief. NOTE: for studies using deception, an alteration of consent must be justified in the Informed Consent section of the protocol (#13) and the debriefing script/statement must be uploaded in the Attachments section (#16).  See IRB Deception Guidelines.

f) Is there an accepted standard of care and/or standard practice at SLU for the condition/disease/situation being studied? This information will assist in comparing the risk/benefit ratio of study procedures relevant to usual care that would be received outside of the research context. **\*?HELP?\*** Y

If yes, please describe the standard of care and standard practice at SLU for the condition/disease/situation being studied.

The smoking cessation program is the standard of care.

g) Does this study involve any diagnostic imaging, labwork or genetic testing that could result in clinical discovery (diagnoses, genetic mutations, etc.)? Note that this could include discovery that is expected (related to the research) or incidental (not related to research aims, but possible, like a mass/shadow found in imaging despite not looking for it). N

If yes, please describe and include whether there are plans to share findings with study participants.

h) Is this study subject to the NIH Genomic Data Sharing Policy? N

The NIH GDS policy applies to all NIH-funded research that generates large-scale human genomic data as well as the use of these data for subsequent research and includes: genome-wide association studies (GWAS), single nucleotide polymorphisms (SNP) arrays, and genome sequence, transcriptomic, metagenomics, epigenomic and gene expression data, irrespective of NIH funding

**Protocol Title:** Smoking Cessation Following Text Message Intervention in Pregnant Women

---

mechanism. [Click here for more specific examples.](#)

---

**\*\*\* Radioisotopes or Radiation Machines \*\*\***

You have not selected the Radioisotopes option in the General Checklist. If you would like to add Radioisotopes information, please select the option to enable this section.

**4. Radioisotopes or Radiation Machines**

In this section, investigators must enter all radiation usage associated with the protocol.

Important: Protocols that involve non-standard of care radioactive materials (which includes the terms "radioisotopes", "radionuclides", "radiopharmaceuticals", and "nuclear medicine studies", e.g., "PET", "MUGA", "Zevalin", and/or specific radionuclides such as "F-18", "Tc-99m", "Th-201", "I-131", "Ra-223", "Y-90", etc.) will receive review by the Radiation Safety Officer (RSO) and/or Radiation Safety Committee (RSC). In these cases, submission to the RSO/RSC should occur first, even before submission to IRB. For more information on how to submit for radiation safety review, see RSC instructions or contact the Radiation Safety Officer at [name].

(1) It is the responsibility of the PI to assure the accuracy and completeness of the data submitted in this section, consistent with guidelines provided below. (2) For projects requiring radiation procedures, please refer to this guidance.

- a) **If applicable, list and quantify the radiographic diagnostic and therapeutic procedures associated with this protocol by clicking "Add" and adding to Table 1 below. (Includes X-ray, fluoroscopy, CT, radioactive materials, nuclear medicine, PET-CT, radiation oncology, accelerator, Cyber Knife procedures, etc.)**

- b) **Total estimated research radiation dose \* :**

\* Calculate from the table above by adding the Effective Dose Subtotals for all procedures.

NOTE: Informed Consent Radiation Exposure Risk Statement- The applicant must insert the appropriate Informed Consent Radiation Exposure Risk Statement template language into the SLU IRB Informed Consent, inclusive of applying the total estimated research radiation dose specified in item b) from the table above, as instructed in the SLU IRB Informed Consent Template. Contact the IRB Office at [name] or [contact] with any questions.

---

**\*\*\* Devices \*\*\***

**Protocol Title:** Smoking Cessation Following Text Message Intervention in Pregnant Women

---

**5. Devices**

- a) Please list in the space below all investigational devices to be used on subjects during this study.
  
  - b) Please list in the space below all FDA approved devices to be used on subjects during this study.
- 

**\*\*\* Drugs, Reagents, Chemicals, or Biologic Products \*\*\***

**6. Drugs, Reagents, Chemicals, Biologic Products, or Dietary Supplements, Vitamins, and Other Food Agents**

Pilot	Phase I	Phase II
Phase III	Phase IV	X Not Phased

List placebo if it is considered a drug (contains more than inactive ingredients). For example, normal saline is considered a drug that should be listed, whereas placebo tablets are usually inert ingredients that do not need to be listed.

- &nb Please list in the space below all investigational drugs, reagents or chemicals to be administered to subjects during this study. Attach all applicable Investigator Brochures in section #16 (Attachments).
  
- &nb Please list in the space below all FDA approved drugs, reagents, chemicals to be administered to subjects during this study. Attach all applicable package inserts in section #16 (Attachments).
  
- &nb Please list in the space below all dietary supplements, vitamins, minerals, or foods to be administered to subjects during this study.

Please read the IND Statements.

---

**\*\*\* Other Levels Of Review \*\*\***

**7. Other Levels Of Review**

**1. University Radiation Safety**

Protocols that involve non-standard of care radioactive materials (which includes the terms "radioisotopes", "radionuclides", "radiopharmaceuticals", and "nuclear medicine studies", e.g., "PET", "MUGA", "Zevalin", and/or specific radionuclides such as "F-18", "Tc-99m", "Th-201", "I-131", "Ra-223", "Y-90", etc.) will receive review by the Radiation Safety Officer (RSO) and/or Radiation Safety Committee (RSC). For information on how to submit for radiation safety review, see RSC instructions or

**Protocol Title:** Smoking Cessation Following Text Message Intervention in Pregnant Women

---

contact the Radiation Safety Officer at [name].

**Not Applicable**

**Yes, study involves radioactive materials (per instructions, submit to RSC before IRB)**

## 2. Institutional Biosafety

Experiments involving the deliberate transfer of Recombinant or Synthetic Nucleic Acid Molecules (e.g., Gene Transfer), or DNA or RNA derived from Recombinant or Synthetic Nucleic Acid Molecules, or Microorganisms containing Recombinant or Synthetic Nucleic Acid Molecules and/or infectious agents (including select agents and toxins as defined by CDC and/or Animal and Plant Health Inspection Service (APHIS)) into one or more human research participants must be reviewed by the SLU Biological Safety Officer. Most of these protocols also require review and approval by the SLU Institutional Biosafety Committee (IBC). Please contact the SLU Biological Safety Officer at [name] for more information.

**Not Applicable**

**Yes, study requires Institutional Biosafety review**

## 3. Pharmacy, Therapeutics, Nutrition, and Transfusion (PTNT) Committee

Saint Louis University Hospital requires that all research involving the administration of medications within the hospital (including outpatient areas such as the Emergency Department, Outpatient Center, Saint Louis University Hospital-South Campus, etc.) be reviewed and approved by the Pharmacy, Therapeutics, Nutrition, and Transfusion (PTNT) Committee and that study drugs are received, stored, prepared, and dispensed by the Hospital's Department of Pharmacy Services. Please contact the Investigational Drug Services Clinical Pharmacist at [name] or [contact] for more information.

**Not Applicable**

**Yes, study requires PTNT review**

## 4. Saint Louis University Hospital

All research involving Saint Louis University Hospital, including inpatient or outpatient services and medical record access, requires approval from the Saint Louis University Hospital Research Review Committee prior to study initiation. This effort is coordinated through the Clinical Trials Office via eRS. This process is designed to facilitate compliance with state and federal regulations as they pertain to research in hospitals and clinical research billing. Documents should be submitted as soon as possible, or at the latest, concurrently with IRB submission. Please contact the Research Compliance Office at [name] or [contact] or the SLU Clinical Trials Office at [name] or [contact] for more information.

**Not Applicable**

**Yes, study requires Saint Louis University Hospital review**

**Protocol Title:** Smoking Cessation Following Text Message Intervention in Pregnant Women

---

**5. SSMSL**

All research involving SSMSL locations (including Cardinal Glennon), including inpatient or outpatient services and medical record access, requires approval from the SSM STL or SSM Cardinal Glennon Research Business Review (RBR) prior to study initiation. This process is designed to facilitate compliance with state and federal regulations as they pertain to research in hospitals and clinical research billing. While researchers can begin to complete the SSM RBR form at any time, the form should not be submitted until the IRB and the CTO have approved the study. Please contact the SSMSL Office at [name] or [name]\[contact] for more information.

**Not Applicable**

- X **Yes, study requires RBR review**

**6. Saint Louis University Department of Marketing**

To list your clinical trial on the SLUCare Marketing website, complete the Clinical Trials Information Form on PDF or online.

- X **I am not interested in SLUCare Marketing services for my study.**

---

**\*\*\* Subject Population \*\*\***

**8. Subject Population - In the space below, please detail the participants that you are requesting to recruit (include description of each group requested)**

- a) **Expected age range of subjects. (For example ≥ 18 yrs to 90 yrs).**

18-55yrs of age

- b) **Number of evaluable subjects to be accrued at SLU or SLU site (this includes all sites under the direction of the SLU PI).**

100

Exceeding the number listed here is a protocol violation. Prior IRB approval is required if additional participants are to be accrued. If applicable, this number should be consistent with your power analysis described in 3d.

- c) **Number of evaluable subjects to be accrued study wide. \*?HELP?\***

100

- d) **If applicable, state the rationale for involvement of potentially vulnerable subjects to be entered into the study, including minors, pregnant women, economically and educationally disadvantaged, or decisionally impaired individuals. Specify the measures being taken to minimize the risks and the chance of harm to the potentially vulnerable subjects.**

The use of pharmacological aids for smoking cessation is recommended as a potential option by the American College of Obstetrics and Gynecology for pregnant women since they are considered safer than continued smoking during pregnancy. . This study will look at adding text messages to see if cessation rates improve.

**Protocol Title:** Smoking Cessation Following Text Message Intervention in Pregnant Women

---

Since this study is looking at pregnant women who smoke we would be unable to perform this study without the inclusion of pregnant women.

- e) **If women, minorities, or minors are not included, a clear compelling rationale must be provided unless not applicable. Examples for not including minors: disease does not occur in children; drug or device would interfere with normal growth and development; etc. If federally funded reference appropriate section of the sponsors protocol/grant. \*?HELP?\***

Minors are excluded from participation because the standard of care medications are not FDA approved for minors.

- f) **If any specifically targeted subjects are students, employees, or laboratory personnel, specify the measures being taken to minimize the risks and the chance of harm to these potentially vulnerable subjects.**

- g) **Describe how potential subjects will be identified for recruitment (e.g., chart review, referral from individual's treating physician, those individuals answering an ad). How will potential participants learn about the research, and how will they be recruited (e.g., flyer, e-mail, web posting, telephone, etc.)? Upload recruitment materials in the Attachment Section (#16). Important to remember: potential subjects cannot be contacted before IRB approval. NOTE: The use of SLU owned websites in an approved SLU format (e.g., Cancer Center website, etc.) are always approved methods of recruitment.**

Potential patients from the MFM practice will be identified through EPIC chart review as well as from referrals from providers. Recruitment flyers will be posted in the MFM clinic area. These patients will be screened for inclusion and exclusion criteria through a chart review as well as meeting with pharmacy to determine the patient's stage of change and willingness to set a quit date within the next 30 days. Informed consent will be obtained if the patient is eligible and willing to participate.

---

**\*\*\* Subject Population \*\*\***

**8. Subject Population (continued)**

**Page numbers from a sponsor's protocol/grant may be referenced in 8h.**

- h) **Inclusion and Exclusion Criteria.**

**Identify inclusion criteria.**

Have a confirmed pregnancy,  
Obstetric care provided at the St. Mary's Health Center Maternal Fetal Care Center,  
English speaking,  
18-55 years of age,  
Are in the preparation stage of change and willing to set a quit date within 30 days and before 35 weeks gestation,  
Have a cellular phone that is capable of receiving text messages, and be willing to pay for any related fees for testing.  
Willing and able to commit to the visit schedule

**Identify exclusion criteria.**

Gestational age > 35 weeks at quit date  
If subjects are in the pre-contemplative or contemplative stages of change or have already received 30

**Protocol Title:** Smoking Cessation Following Text Message Intervention in Pregnant Women

---

minute pharmacy education targeted for the quit date in this pregnancy.

- i) **Compensation. Explain the amount and schedule of compensation, if any, that will be paid for participation in the study. Include provisions for prorating payment.**

No compensation will be paid to the subject

- j) **Describe who will cover study related costs. Explain any costs that will be charged to the subject.**

The carbon monoxide testing will be paid for by St. Louis College of Pharmacy.

All pharmacotherapy, although standard of care will be provided by the College of Pharmacy.  
All visits are standard of care and will not be paid for by the study.  
Subjects will be advised prior to consenting that if their phone plan charges for receiving text messages, the study will not pay for those charges.  
No study related costs will be billed to the subject or their insurance.

- k) **Estimate the probable duration of the entire study including data analysis and publication. This estimate should include the total time each subject is to be involved and the duration the data about the subject is to be collected. If the study is Investigator-initiated, a timeline for individual subject recruitment, follow-up, total time for subject accrual, and data analysis for the study is required.**

Subject participation will vary depending on when in her pregnancy a subject enrolls.  
March 2014: Obtain IRB approval  
April 1 2014: Begin enrolling patients via randomization  
April 31st, 2015: Cease enrollment of new patients  
June 1st 2015: Final collection of all data for all enrolled patients  
Summer 2015: Data analysis, manuscript preparation

---

\* \* \* Risks \* \* \*

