The primary objective of the study is to evaluate the impact of a text-message service on smoking cessation in medically underserved, obstetric patients when added to the usual care of pharmacist-driven CBT smoking cessation program and smoking cessation pharmacotherapy with either the nicotine replacement patch or bupropion. The smoking cessation rate will be verified by exhaled carbon monoxide levels (<8ppm) at 2 weeks of the patients quit date. Secondary objectives of the study include (1) a comparison of self-reported cessation versus verified cessation from the exhaled carbon monoxide level, (2) self-reported cessation rates at 1 month, 3 months, and delivery as verified by exhaled carbon monoxide levels, and (3) change in exhaled carbon monoxide levels from baseline to 2 week follow-up, (4), to better understand which patients may face additional barriers with tobacco cessation during pregnancy and ongoing use of marijuana and alcohol may be predictive.

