**Please save frequently**

- c) Describe the study design (e.g., single/double blind, parallel, crossover, control, experimental, observational, etc.). If the study is investigator-initiated, a timeline for individual subject recruitment, follow-up, and analysis for the study is required. Also, indicate if the subjects will be randomized.

**Protocol Title:** Smoking Cessation Following Text Message Intervention in Pregnant Women

---

We propose an 18-month prospective, randomized, open-label evaluation of the impact of texting to pregnant, underserved, cigarette smokers on smoking cessation rates.

March 2014: Obtain IRB approval  
 April 1 2014: Begin enrolling patients via randomization  
 April 31st, 2015: Cease enrollment of new patients  
 June 1st 2015: Final collection of all data for all enrolled patients  
 Summer 2015: Data analysis, manuscript preparation

d) **If subjects will be given placebo, please justify placebo use. \*?HELP?\***

N/A

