**If No, explain what SLU will NOT participate in:**

**Please save frequently**

Page numbers from a sponsor's protocol/grant may be referenced in 3b, 3c, and 3d.

- b) **Describe all the procedures, from screening through end-of-study, that the human subject must undergo in the research project, including study visits, drug treatments, randomization and the procedures that are part of standard of care. Specify which procedures are for research and which are standard of care. Please note: The box below is for text only. If you would like to add tables, charts, etc., attach those files in the Attachment section (#16).**

This is a randomized, open-label, prospective trial that will evaluate the impact of texting to pregnant, underserved, cigarette smokers on smoking cessation rates. It will be conducted over 18-months, with subject recruitment over 12 months, at St. Mary's Health Center Maternal Fetal Care Center. Potential patients will be identified through EPIC chart review as well as from referrals from providers. These patients will be screened for inclusion and exclusion criteria through a chart review as well as meeting with pharmacy to determine the patient's stage of change and willingness to set a quit date within the next 30 days. Informed consent will be obtained if the patient is eligible and willing to participate.

As part of routine care at the Maternal Fetal Care Center, pregnant women that are active smokers are encouraged to quit. If the patient is interested in quitting smoking, the physician or pharmacist will schedule a smoking-cessation consultation visit with maternal-fetal clinical pharmacist. During this pilot study, women who have expressed interest in quitting and meet the inclusion and exclusion criteria will be approached and offered enrollment in the smoking cessation study. Patients who consent will be randomized to either the texting group or control group. For randomization purposes, an equal number of notecards will be made for the two groups. We will use a random number generator to help with patient randomization. These

**Protocol Title:** Smoking Cessation Following Text Message Intervention in Pregnant Women

---

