groups. We will use a random number generator to help with patient randomization. These numbers will be placed in a sealed envelope and shuffled. At the time of patient inclusion, an envelope will be selected by the pharmacist. However, if a patient declines receiving text messages but consents to participate in the pharmacist driven CBT and NRT, she will be enrolled in the standard of care group. A baseline carbon monoxide level will be obtained.

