#### Description of Usual Care

The patient, regardless of group, will have the standard of care smoking cessation visit with the clinical pharmacy specialist or PGY2 ambulatory care resident. The visit will include

- Medication reconciliation
- Review social history which includes use of street drugs and alcohol, allergies, and vaccine history
- Obtain smoking history that included current amount smoking, changes in smoking habits during this pregnancy, number of years smoked, quit attempt history, and use of previous smoking cessation aids
- Design a quit plan that includes setting a quit date within the next 30 days, obtain follow-up contact information, identify motivators/triggers/barriers, discuss withdrawal symptoms, develop plan for management of withdrawal symptoms, develop a plan for behavior modifications, discuss rewards, handling of relapse, medication options for cessation during pregnancy, and education on purpose, proper use, potential maternal and neonatal adverse events

If the pharmacist, physician, and patient deem that pharmacotherapy is appropriate, the patient will receive a 2 week supply if using NRT or 3 week supply if using bupropion. The smoking cessation pharmacotherapy will be supplied free of charge to the consenting participants. If the patient is prescribed NRT patches, the medication will be provided in two week intervals. If the patient is prescribed bupropion, the medication will be provided for a 3 week supply with the initial dispensing and 2 week supply thereafter. Dosing and length of treatment will follow package insert approved dosing. Patients will receive a voucher to take to the Clayton Health Services Pharmacy located across the street from the Maternal Fetal Care Clinic to receive either medication at no cost.

Demographics, social history, gestation age at enrollment, estimated due date, medications at enrollment, past medical history, and obstetric history include gravity and parity will be obtained from the EPIC medical record. Patients will be asked about smoking history, time to first morning cigarette, previous quit attempts, previous experience with cessation pharmacotherapy, motivators, triggers, and barriers during initial visit.

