#### Follow-up phone calls and visits for Intervention and Control Groups

Usual follow-up includes a telephone call to the patient within 3 days of the quit date then weekly for 2 weeks afterwards. Each phone call includes assessing current smoking status, identifying withdrawal symptoms and how the patient handles them, review of behavior modifications, assessment of reward planning, medication reconciliation, assessment for adherence, concerns, and adverse events with therapy, and education as needed on the above areas.

Patients will be scheduled to return to the Maternal Fetal Care Clinic 2-weeks after their quit date to obtain additional voucher to refill patches or bupropion. At each voucher pick-up, the patient will need to report her smoking status then perform an exhaled carbon monoxide level.

**Protocol Title:** Smoking Cessation Following Text Message Intervention in Pregnant Women

---

Patients will be continued to be seen on a bi-weekly schedule to obtain additional vouchers for patches or for bupropion, meet with the pharmacist, and complete a carbon monoxide exhalation test. These visits will be continued until the pharmacotherapy course is complete.

As the only intervention in this study is text messaging and the primary outcome measure is smoking cessation, we plan to continue the study through the patient's delivery. The patient may discontinue enrollment at any time.

Text Message Intervention  
Smoking Cessation Text Messages

\*Prior to quit date

\*Inform others:

Congratulations, your quit date is in 3 days! Let friends and family know you are planning to quit and how they can help support you. Support is one of the key pieces to quitting smoking!

\* Remove reminders:

Congratulations, your quit date is in 2 days! Get rid of things such as lighters, ashtrays, and cigarettes. Clean your car, house, and clothes so they don't smell like cigarette smoke when you quit.

\*Prepare for cravings:

Congratulations, your quit date is tomorrow! Remember that cravings will only last about 20 minutes, so have activities planned to distract yourself! Do a crossword puzzle, take a walk, clean the house, eat a healthy snack if you're hungry, etc.

\* Reasons why you're quitting

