**b) Hardcopy (Paper) Data**

Click "Add" to enter information for each type of hardcopy (paper) data that will be created in the study: anonymous/de-identified, coded, and/or identifiable (see definitions above).

To properly address this question, there should only be one listing of each type of data in the table. Depending on your project, you could have up to three types of data.

Not Applicable, No Hardcopy (Paper) Data

Study IRB-approved Prior to New Question (Question N/A- Grandfathered)

**c) If a master list is used in this study (linking study codes to subject identifiers), explain: a) how and where you will secure the master list, b) how long it will be kept/when it will be destroyed, and c) provide a sample of the code.**

Code numbers will be used to link the subject to their data. Code and identifiers will be kept separate. PHI will be password protected behind a firewall. Paper copies will be kept in a locked cabinet, in a locked

**Protocol Title:** Smoking Cessation Following Text Message Intervention in Pregnant Women

---

office, in a locked suite.

After data is entered into the database, the paper copy of the data will be destroyed.

A master list is kept to link the medical record information to the subject and to obtain follow up information (delivery). The master list is kept separate from the data and will be destroyed when the study is complete.

**d)&n bsp If data or specimens are being shared outside of the research team, indicate who will receive the material and specifically what they will receive (data or specimens).**

The only patient information stored in the Google Voice system will be a phone number which will be identified by a unique participation number for each patient upon her inclusion in the study. The Google Voice system is password protected and only one person will have the password.

The St. Louis College of Pharmacy's IRB provides oversight and may require review of the research records, including patient information.

**e) If samples or data will be provided from an outside source, indicate whether you will have access to identifiers, and if so, how identifiable information is protected.**

N/A

**f) If data will be collected via e-mail or the Internet, how will anonymity or confidentiality be affected? Describe how data will be recorded (i.e., will internet protocol (IP) addresses and/or e-mail addresses be removed from data?).**

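### Data collection for all women closes on June 1st 2015, too soon after enrolment ends for later enrolees to reach the 3-month and delivery outcomes, and the stated recruitment length disagrees with the listed dates

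*Combined protocol and SAP*

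**What the plan says.** Sections 2c and 8k of the combined protocol and SAP carry the same timeline. Enrolment begins on April 1 2014. It ends on a date that does not exist, "April 31st, 2015: Cease enrollment of new patients", and then comes "June 1st 2015: Final collection of all data for all enrolled patients". Analysis follows in summer 2015. Section 3b describes an 18-month study "with subject recruitment over 12 months".

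Section 2b lists among the secondary objectives "self-reported cessation rates at 1 month, 3 months, and delivery as verified by exhaled carbon monoxide levels". Section 3b, under follow-up calls and visits, says "we plan to continue the study through the" patient's delivery. Section 11c keeps the master list so that delivery follow-up can be obtained. Section 8k adds that each woman's time in the study depends on when in pregnancy she enrols.

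Section 8h lets the quit date fall up to 30 days ahead and requires it to be before 35 weeks' gestation. The sections shown give no rule for outcomes not reached by June 1st 2015.

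**The concern.** One calendar date ends collection for every woman, while follow-up is promised to a time point of her own. A gap of 32 days cannot hold a 3-month outcome for the last enrolees, and it cannot hold most of a pregnancy. The 62-day gap under 12-month recruitment is still short of 3 months.

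What is at stake is the second secondary objective. Its 3-month and delivery results would rest on a reduced denominator that nobody planned. The women seen at delivery would also tilt, in both arms, towards those who enrolled later in pregnancy.

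**Working it through.** **Inputs.** Enrolment starts April 1 2014 and collection ends June 1 2015 (sections 2c, 8k). April 31st is read as April 30 2015. The variant with 12-month recruitment (section 3b) ends March 31 2015. The quit date is 0 to 30 days after enrolment (section 8h). Three months is taken as 91 days. Two quantities are assumed because the documents do not give them: accrual is even, and gestation at enrolment is shown as a range. Delivery is taken at 37 to 40 weeks.

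**Recruitment length.** April 1 2014 to April 30 2015 is 395 days inclusive, or 13 months; to March 31 2015 it is 365 days, or 12 months. The stated 12 months is therefore not reproduced from the listed dates. No section writes 13 months; it follows from the dates.

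**Gap to June 1.** 32 days from April 30; 62 days from March 31.

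**Share cut off.** With lag = days from enrolment to the outcome, days lost = max(0, lag − gap), and share = days lost / accrual days.

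| Outcome (quit date at enrolment, then 30 days later) | Lag, days | 13-month recruitment | 12-month recruitment |
|---|---|---|---|
| 2 weeks (primary) | 14, 44 | 0; 12/395 = 3.0% | 0; 0 |
| 1 month | 30, 60 | 0; 28/395 = 7.1% | 0; 0 |
| 3 months | 91, 121 | 59/395 = 14.9%; 89/395 = 22.5% | 29/365 = 7.9%; 59/365 = 16.2% |

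The last enrolment date that still reaches 3 months by June 1 is March 2 2015 with an immediate quit date, and January 31 2015 with a quit date 30 days later. The 3-month shares correspond to about 9 to 14 (12-month: 5 to 10) of the 60 women in section 3d, or 15 to 23 (8 to 16) of the 100 in sections 8b and 8c.

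**Why the 3-month figures are upper bounds.** Three months is 13 weeks, and 40 − 13 = 27. A woman whose quit date falls after about 27 weeks passes a 40-week delivery before 3 months, so June 1 is not what takes her outside follow-up through delivery.

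**Delivery.** Lag = (37 or 40 − weeks at enrolment) × 7. For example, enrolled at 8 weeks and delivering at 40: 32 × 7 = 224; 224 − 32 = 192; 192/395 = 48.6%.

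| Weeks at enrolment | Days lost of 395 | Share | Days lost of 365 | Share |
|---|---|---|---|---|
| 8 | 171 to 192 | 43.3% to 48.6% | 141 to 162 | 38.6% to 44.4% |
| 12 | 143 to 164 | 36.2% to 41.5% | 113 to 134 | 31.0% to 36.7% |
| 20 | 87 to 108 | 22.0% to 27.3% | 57 to 78 | 15.6% to 21.4% |
| 28 | 31 to 52 | 7.8% to 13.2% | 1 to 22 | 0.3% to 6.0% |
| 34 | 0 to 10 | 0% to 2.5% | 0 | 0% |

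To reach 40 weeks by June 1, a woman enrolled on April 30 would need to be at 280 − 32 = 248 days, or 35 weeks 3 days. That is past the 35-week limit on the quit date.

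**The case against.** The best defence is that June 1 is a forecast. Section 8k asks for an estimate of probable duration, section 3b gives each woman an end point of her own (delivery), and the master list is kept for delivery follow-up. On that reading collection would simply run on. This is plausible, and it is why the point concerns the plan as written and does not claim that data were lost. It does not remove the conflict: both timelines apply June 1 to all enrolled women, and the 8k prompt says that a follow-up timeline is required of investigator-initiated studies.

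It is also fair that the size at delivery depends on gestation at enrolment, which is unknown, and runs from almost nothing to nearly half. The range has to be shown; no single figure is supported.

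There are other gaps for the same outcomes. Section 3b ties breath tests to voucher visits and lists only obstetric details at delivery, and section 3d names no test for this objective. The data collection sheets are not shown. These are separate matters and do not excuse the date.

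A reader might infer three stronger things that the documents do not support:

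- **Bias between arms.** The cut-off is set by the calendar and is expected to fall on both arms alike.
- **A compromised primary outcome.** Only women enrolled after April 18 2015 with a late quit date are exposed.
- **A contradiction in the 18-month total.** March 2014 to August 2015 is 18 months.

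**Conclusion.** The conflict is real and should be corrected, but it is confined to secondary outcomes. With even accrual, and figures for 12-month recruitment in brackets, at most 15% to 23% (8% to 16%) of women miss 3 months because of the date. The loss at delivery is 43% to 49% (39% to 44%) for women enrolled at 8 weeks, 22% to 27% (16% to 21%) at 20 weeks and 0% to 2.5% (0%) at 34 weeks. The primary outcome loses at most 3% (0%). That some late enrolees cannot reach 3 months by June 1 needs no assumption about gestation; the percentages rest on even accrual and, for delivery, on the gestations assumed.

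**What to change.** 1. Reconcile the recruitment period in sections 2c, 3b and 8k, and replace April 31st with a real date.
2. Replace June 1st 2015 with a rule: collection closes when the last of the enrolled women has delivered, which matches section 3b.
3. State whether the 3-month outcome applies to women who deliver before 3 months. If it does, say so openly as postpartum follow-up, which section 3b does not describe, and let collection run to the later of the two points. The last 3-month point would be August 29 2015 (July 30 with 12-month recruitment).

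This needs wording changes and no extra women. The cost is a later secondary analysis: delivery data could close as late as December 10 2015 (November 10) for a woman enrolled last at 8 weeks who delivers at 40. The primary analysis need not wait, since its last point is June 13 2015 (May 14).

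**If June 1 is kept or has already been applied.** The expedited-review page marks the remaining work as data analysis only, so new breath tests may no longer be possible. Then report 3-month and delivery results by arm on denominators fixed at enrolment:

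- 3 months: women enrolled on or before January 31 2015.
- Delivery: women whose estimated due date, recorded at enrolment, is on or before June 1 2015, counting any still undelivered then as missing.

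Do not define either set by quit date. Section 3b says "At the time of patient inclusion, an envelope will be selected by the pharmacist", and the usual-care visit described after it is where staff "Design a quit plan that includes setting a quit date within the next 30 days", so in this open-label trial the quit date appears to be set after allocation.

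State how many women the calendar cut off, and disclose what these sets keep. At 3 months it is 306/395, about 77% (306/365, 84%). At delivery, taking 100% minus the 40-week losses, it is about 51% (56%) of women enrolled at 8 weeks, 58% (63%) at 12 weeks and 73% (79%) at 20 weeks. The delivery set therefore still tilts towards women enrolled later in pregnancy; the fallback makes the loss visible but does not repair it.
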